5.7 Diet/Activity/Other Considerations

5.7.1 Diet

Subjects should maintain a normal diet unless modifications are required to manage an AE such as diarrhea, nausea or vomiting.

5.7.2 Contraception

MK-3475 may have adverse effects on a fetus in utero. Furthermore, it is not known if MK-3475 has transient adverse effects on the composition of sperm. Non-pregnant, non-breast-feeding women may be enrolled if they are willing to use 2 methods of birth control or are considered highly unlikely to conceive. Highly unlikely to conceive is defined as 1) surgically sterilized, or 2) postmenopausal (a woman who is ≥ 45 years of age and has not had menses for greater than 1 year will be considered postmenopausal), or 3) not heterosexually active for the duration of the study. The two birth control methods can be either two barrier methods or a barrier method plus a hormonal method to prevent pregnancy. Subjects should start using birth control from study Visit 1 throughout the study period up to 120 days after the last dose of study therapy.

The following are considered adequate barrier methods of contraception: diaphragm, condom (by the partner), copper intrauterine device, sponge, or spermicide. Appropriate hormonal contraceptives will include any registered and marketed contraceptive agent that contains an estrogen and/or a progestational agent (including oral, subcutaneous, intrauterine, or intramuscular agents).

Subjects should be informed that taking the study medication may involve unknown risks to the fetus (unborn baby) if pregnancy were to occur during the study. In order to participate in the study they must adhere to the contraception requirement (described above) for the duration of the study and during the follow-up period defined in section 7.2.2-Reporting of Pregnancy and Lactation to the Sponsor and to Merck. If there is any question that a subject will not reliably comply with the requirements for contraception, that subject should not be entered into the study.

5.7.3 Use in Pregnancy

If a subject inadvertently becomes pregnant while on treatment with MK-3475, the subject will immediately be removed from the study. The site will contact the subject at least monthly and document the subject's status until the pregnancy has been completed or terminated. The outcome of the pregnancy will be reported to the Sponsor and to Merck without delay and within 24 hours if the outcome is a serious adverse experience (e.g., death, abortion, congenital anomaly, or other disabling or life-threatening complication to the mother or newborn). The study investigator will make every effort to obtain permission to follow the outcome of the pregnancy and report the condition of the fetus or newborn to the Sponsor. If a male subject impregnates his female partner the study personnel at the site must be informed immediately and the pregnancy reported to the Sponsor and to Merck and followed as described above and in Section 7.2.2.

5.7.4 Use in Nursing Women

It is unknown whether MK-3475 is excreted in human milk. Since many drugs are excreted in human milk, and because of the potential for serious adverse reactions in the nursing infant, subjects who are breast-feeding are not eligible for enrollment.

5.8 Subject Withdrawal/Discontinuation Criteria

Subjects may withdraw consent at any time for any reason or be dropped from the trial at the discretion of the investigator should any untoward effect occur. In addition, a subject may be withdrawn by the investigator or the Sponsor if enrollment into the trial is inappropriate, the trial plan is violated, or for administrative and/or other safety reasons. Specific details regarding discontinuation or withdrawal are provided in Section 7.1.3 – Other Procedures.

A subject must be discontinued from the trial for any of the following reasons:

- The subject or legal representative (such as a parent or legal guardian) withdraws consent.
- Confirmed radiographic disease progression

Note: For unconfirmed radiographic disease progression, please see Section 5.2.2

Note: A subject may be granted an exception to continue on treatment with confirmed radiographic progression if clinically stable or clinically improved, please see Section 7.1.2.7.1

- Unacceptable adverse experiences as described in Section 5.2.1.2
- Intercurrent illness that prevents further administration of treatment
- Investigator's decision to withdraw the subject
- The subject has a confirmed positive serum pregnancy test
- Noncompliance with trial treatment or procedure requirements
- The subject is lost to follow-up
- Completed 24 months of treatment with MK-3475

Note: 24 months of study medication is calculated from the date of first dose. Subjects who stop MK-3475 after 24 months may be eligible for up to one year of additional study treatment if they progress after stopping study treatment provided they meet the requirements detailed in Section 7.1.5.2.1.

- Administrative reasons

The End of Treatment and Follow-up visit procedures are listed in Section 6 (Protocol Flow Chart) and Section 7.1.5 (Visit Requirements). After the end of treatment, each subject will be followed for 30 days for adverse event monitoring (serious adverse events will be collected for 90 days after the end of treatment as described in Section 7.2.3.1). Subjects who discontinue for reasons other than progressive disease will have post-treatment follow-up for

disease status until disease progression, initiating a non-study cancer treatment, withdrawing consent or becoming lost to follow-up. After documented disease progression each subject will be followed by telephone for overall survival until death, withdrawal of consent, or the end of the study, whichever occurs first.

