2.2 Trial Diagram

- For Part A we will allow induction chemotherapy
- Primary Endpoint
 - Safety
- Secondary endpoint
 - Improvement in PFS compared to historical controls

[figure not shown]
Part A: Is only for patients with Limited Stage SCLC, we will allow induction chemotherapy. The total cycles of chemotherapy recommended will be 4, as such if a patient had two cycles of induction chemotherapy they would only get an additional two with MK-3475. PCI will be allowed based on the treating physician discretion and will be done after chemotherapy has been completed. PCI will delay the next dose of MK-3475 by one cycle and PCI should start approximately three weeks after MK-3475. MK-3475 can be resumed following the completion of PCI. LS-SCLC patients, who achieve systemic disease control during/after completion of 16 cycles of MK-3475, will be eligible to get additional 16 cycles of MK-3475, provided they did not exhibit severe (grade >3) MK-3475 related toxicity during therapy. Systemic disease control is defined as stable disease or partial response or complete response, based on irRC criteria.

Part A for LS-SCLC

* Eligible patients may receive additional 16 cycles.

Part B: Is only for patients with Extensive Stage SCLC who are receiving consolidation XRT after 1-6 cycles of chemotherapy. Patients needing PCI are encouraged to have it completed prior to enrollment in this trial. If PCI needs to be given on study, after thoracic XRT, then it should be done in a manner consistent with part A. PCI will delay the next dose of MK-3475 by one cycle and PCI should start approximately three weeks after MK-3475. MK-3475 can be resumed following the completion of PCI.) Patients needing XRT treatment to other sites outside the thorax will be allowed, but is encouraged to be done prior to starting the trial.

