4.2.3 Rationale for Endpoints

4.2.3.1 Efficacy Endpoints

Part A LS-SCLC: The primary endpoint is safety in order to establish the MTD of MK-3475 with concurrent chemo and radiation. The primary acute toxicity for chemo and radiation is esophagitis with a rate of $\geq 32\%$ ⁸. While the long term toxicity rate of grade 3 pneumonitis is around 13%⁹.

Part B ES-SCLC: The primary endpoint is safety in order to establish the MTD of MK-3475 with concurrent radiation. The primary acute toxicity for chemo and radiation is esophagitis with a rate of $\geq 32\%$ ⁸. While the long term toxicity rate of grade 3 pneumonitis is around 13%⁹.

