6.0 TRIAL FLOW CHART

6.1 Study Flow Chart (All scheduled tests will be given a window of +/- 3 days)

Treatment Cycle/Title:	Main Study Screening	1	2	3	4	5	6-16 (additional 16 cycles, for eligible patients)	Post MK-3475 Follow up	Survival Follow-Up (>2yrs) ^a
Scheduling Window (Days):	-28 to -1		± 3	± 3	± 3	± 3	± 3	Every 12 weeks post discon	Every 12 weeks
Administrative Procedures									
Informed Consent	X								
Medical History	X								
Concomitant Medication Review	X	X	X	X	X	X	X	X ^a	
Trial Treatment Administration		X	X	X	X	X	X		
Survival Status								X ^{a, f}	X ^{a, f}
Clinical Procedures/Assessments									
Review Adverse Events		X	X	X	X	X	X		
Directed Physical Examination	X	X	X	X	X	X	X		
Vital Signs and Weight	X	X	X	X	X	X	X		
ECOG Performance Status	X								
Laboratory Procedures/Assessments: Analysis Performed by LOCAL Laboratory									
Pregnancy Test – Urine or Serum β-HCG	X ^d								
PT/INR and aPTT	X								
CBC with Differential	X	X ^f							
Comprehensive Serum Chemistry Panel (BMP)	X	X	X	X	X	X	X		
T3, FT4 and TSH ^b	X ^b		X ^b		X ^b		X ^b		
PFT's	X							X ^{c, f}	
Biopsy ^e		X ^g							

Treatment Cycle/Title:	Main Study Screening	1	2	3	4	5	6-16 (additional 16 cycles, for eligible patients)	Post MK-3475 Follow up	Survival Follow-Up (>2yrs) ^a
Scheduling Window (Days):	-28 to -1		± 3	± 3	± 3	± 3	± 3	Every 12 weeks post discon	Every 12 weeks
Blood Biomarker Testing ^e	X	X	X	X	X	X	X	X	
Efficacy Measurements									
Tumor Imaging (CT or PET scan) ^e	X				X		X ^f	X ^{e, f}	X ^{e, f}

- a. Can be done over the phone.
- b. Thyroid functions will be performed with every other MK-3475 cycle, if the first three test are WNL then it can be stopped.
- c. Optional biopsy after radiation treatment
- d. Within 2 weeks of study entry for women with child bearing potential.
- e. Imaging should be performed approximately every 12 weeks (± 4 weeks).
- f. standard of care
- g. Within 3 months of study entry

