7.1.3 Other Procedures

7.1.3.1 Withdrawal/Discontinuation

When a subject discontinues/withdraws prior to trial completion, all applicable activities scheduled for the final trial visit should be performed at the time of discontinuation. Any adverse events which are present at the time of discontinuation/withdrawal should be followed in accordance with the safety requirements outlined in Section 7.2 - Assessing and Recording Adverse Events. Subjects who a) attain a CR or b) complete 24 months of treatment with MK-3475 may discontinue treatment with the option of restarting treatment if they meet the criteria specified. After discontinuing treatment following assessment of CR, these subjects should return to the site for a Safety Follow-up Visit (described in Section 7.1.5.3.1) and then proceed to the Follow-Up Period of the study (described in Section 7.1.4.4).

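### The MK-3475 treatment limits and the retreatment and restart rules disagree between sections, and the section cited for retreatment is not in the document

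*Combined protocol and SAP*

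**What the plan says.** Six places bear on how long MK-3475 may be given.

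- **Section 5.2, Table 2:** 16 cycles at 3-week intervals. No part is named and no extension is mentioned.
- **Section 2.2:** LS-SCLC patients with systemic disease control and no severe related toxicity "will be eligible to get additional 16 cycles of MK-3475". The Part B paragraph gives no extension.
- **Section 6.1 flow chart:** one chart serves both parts. Its column is headed "6-16 (additional 16 cycles, for eligible patients", and no part is named.
- **Section 5.8:** lists "Completed 24 months of treatment with MK-3475" among the reasons why a subject *must* be discontinued and adds that "24 months of study medication is calculated from the date of first dose". The same note says that subjects who stop after 24 months "may be eligible for up to one year of additional study treatment if they progress after stopping study treatment", subject to requirements in Section 7.1.5.2.1.
- **Section 7.1.3.1:** subjects who reach a CR, or who "complete 24 months of treatment with MK-3475 may discontinue treatment with the option of restarting treatment if they meet the criteria specified". The criteria are not given there or elsewhere.
- **Section 5.4.2:** mentions in passing a retreatment period for relapse after complete response, also without criteria.

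Two places say what happens after progression. The end of Section 5.8 and Section 7.1.4.4.1 both place the patient in survival follow-up by telephone.

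**The concern.** The cycle-based limits (Table 2, Section 2.2) and the calendar limit with a further year (Sections 5.8 and 7.1.3.1) read as two different treatment plans. Section 5.8 does not list completion of 16 or 32 cycles as a reason to stop; 24 months is its only duration limit. It makes stopping at that point compulsory, while Section 7.1.3.1 makes it optional.

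The retreatment provision is the more serious part. It permits further infusions of study drug in patients whose disease has progressed, yet the document holds no eligibility rule, visit schedule or safety assessment for them. The collection windows for AEs (Section 7.2, 30 days) and SAEs (Section 7.2.3.1, 90 days) run from cessation of treatment. Once treatment can stop and restart, it is unclear which cessation is meant.

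**Working it through.** **Inputs.** Interval 3 weeks (21 days) and base course 16 cycles, from Table 2. Extension of 16 cycles, from Section 2.2. Limit of 24 months from first dose and a further 12 months, from Section 5.8. Toxicity may lengthen the interval by a week (Table 3), and PCI delays the next dose by one cycle (Section 2.2). DLT window 22 days, from Section 9.1. One month is taken as 365.25/12 = 30.4375 days. The plan gives no figure that rests on treatment duration, so there is none to reproduce.

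**Step 1: one scale.** Days = cycles × 21; months = days / 30.4375.

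| Rule | Days | Weeks | Months | Cycle lengths |
|---|---|---|---|---|
| 16 cycles | 336 | 48 | 11.0 | 16 |
| 32 cycles | 672 | 96 | 22.1 | 32 |
| 24 months | 730.5 | 104.4 | 24 | 34.8 |
| Further 12 months | 365.25 | 52.2 | 12 | 17.4 |

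**Step 2: is 24 months compatible with Part A?** 24 − 22.1 = 1.9 months, or 104.4 − 96 = 8.4 weeks of slack. That covers a PCI delay of 3 weeks and some holds. With every interval at 4 weeks, 32 cycles would take 32 × 28 / 30.4375 = 29.4 months and the calendar limit would act first. Read as a calendar cap, it is coherent.

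**Step 3: is it compatible with Part B?** 24 − 11.0 = 13.0 months. For 16 cycles to last 24 months the mean interval would have to be 104.4 / 16 = 6.5 weeks. With every interval at 4 weeks they last 16 × 28 / 30.4375 = 14.7 months. The limit is practically unreachable without long holds.

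**Step 4: does the extra year fit?** 16 + 17.4 = 33.4 cycles against a limit of 16; 32 + 17.4 = 49.4 against a limit of 32. It fits neither. Entry is also uneven. A Part A patient who completes 32 cycles on schedule stops at 22.1 months and does not meet the 24-month condition; one delayed by more than 8.4 weeks does. The CR route in Section 7.1.3.1 has no 24-month condition, so it is open to both parts, and no length is stated for it.

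**Step 5: can the cited rules be found?** Visit requirements are numbered 7.1.4. The only heading that begins 7.1.5 is 7.1.5.3.1, the safety follow-up visit. Nothing in that stretch is marked as removed. The flow chart has no retreatment column.

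**Step 6: what depends on duration?**

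- *DLTs:* the window is 22 days under every rule (22/336 = 6.5% of a 16-cycle course, 22/672 = 3.3% of a 32-cycle course). Nothing changes.
- *PFS:* the extra year begins only after progression, so the event has already been counted. Section 5.4.2 describes the post-CR case as relapse, to which the same applies.
- *AE collection:* counted from the first cessation, the 30-day window closes before a later restart, and unrelated SAEs after 90 days fall outside Section 7.2.3.1. Counted from the last cessation, collection would have to reopen, and no text says that it does.
- *AE tables:* Section 9.2.3 tabulates by grade, type and dose or cohort. It does not say how events in an extension or restart are counted.

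**The case against.** The strongest defence is that most of the durations can be read together, and much of it stands.

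- Sixteen versus 32 cycles is a base course plus a stated, conditional Part A extension. Section 2.2 defines who is eligible, and the flow chart appears to borrow that term. What remains is Table 2's silence and a shared chart that does not name the part.
- A reader might infer that Part B patients face either 48 weeks or 24 months of dosing, a gap of 104.4 − 48 = 56.4 weeks or nearly 19 doses. The documents do not support this. Section 5.8 sets a stop and does not prescribe dosing up to it, and no section gives Part B more than 16 cycles.
- A reader might also infer that the primary endpoint is undermined. Section 4.2.3.1 says of Part A that "The primary endpoint is safety in order to establish the MTD of MK-3475 with concurrent chemo and radiation", and Part B is worded in parallel. Escalation and the expansion-cohort rule rest on early toxicity with a 22-day DLT window, so dose finding is unaffected.
- Nor does retreatment after progression bias PFS, which is in any case only described (Section 9.2.4).
- Related SAEs remain reportable at any time (Section 7.2.3.1), so the AE gap is not total.

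The defence does not reach the retreatment text. The extra year exceeds both cycle limits, its rules are missing, *must* and *may* disagree, and telephone follow-up is incompatible with giving infusions to the same patient.

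**Conclusion.** The inconsistency is real and should be corrected before any patient is extended or restarted. The stated limits are 11.0 months (16 cycles), 22.1 months (32 cycles, Part A only) and 24 months. The last can be read as a cap in Part A and is practically idle in Part B. The further year, about 17 cycles, belongs to neither cycle-based plan and has no operating rules in the document. The consequences are confined to cumulative exposure, the safety monitoring of any retreated patient, and the meaning of AE and SAE windows counted from cessation. The MTD, the DLT rules and PFS are not put in doubt.

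The durations assume the 3-week schedule except where a longer interval is shown. The number of patients who would be retreated cannot be estimated from the documents. This review takes no view on which duration or retreatment rule is right.

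**What to change.** 1. Reconcile Section 2.2, Table 2, Section 5.4.2, Section 5.8, the flow chart and Section 7.1.3.1 so that each part has one stated treatment limit. State whether the 24 months is a cap on that limit, and make *must* and *may* discontinue agree.
2. Either delete the retreatment and restart text, or supply the cited section with its eligibility, visit and safety-assessment rules and align it with the follow-up text at the end of Section 5.8 and in Section 7.1.4.4.1.
3. State in Sections 7.2 and 9.2.3 which cessation of treatment starts the AE and SAE windows, and how the AE tables count events during an extension or restart.

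The choice of rule is the sponsor's. Deletion costs only a wording amendment. Supplying a retreatment section also adds assessments for any patient retreated. Neither changes the sample size or the dose-finding rules.

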5.9 Subject Replacement Strategy

5.10 Clinical Criteria for Early Trial Termination

Early trial termination will be the result of the criteria specified below:

1. Quality or quantity of data recording is inaccurate or incomplete
2. Poor adherence to protocol and regulatory requirements
3. Incidence or severity of adverse drug reaction in this or other studies indicates a potential health hazard to subjects
4. Plans to modify or discontinue the development of the study drug

In the event of Merck decision to no longer supply study drug, ample notification will be provided so that appropriate adjustments to subject treatment can be made.

6.0 TRIAL FLOW CHART

6.1 Study Flow Chart (All scheduled tests will be given a window of +/- 3 days)

Treatment Cycle/Title:	Main Study Screening	1	2	3	4	5	6-16 (additional 16 cycles, for eligible patients)	Post MK-3475 Follow up	Survival Follow-Up (>2yrs) ^a
Scheduling Window (Days):	-28 to -1		± 3	± 3	± 3	± 3	± 3	Every 12 weeks post discon	Every 12 weeks
Administrative Procedures									
Informed Consent	X								
Medical History	X								
Concomitant Medication Review	X	X	X	X	X	X	X	X ^a	
Trial Treatment Administration		X	X	X	X	X	X		
Survival Status								X ^{a, f}	X ^{a, f}
Clinical Procedures/Assessments									
Review Adverse Events		X	X	X	X	X	X		
Directed Physical Examination	X	X	X	X	X	X	X		
Vital Signs and Weight	X	X	X	X	X	X	X		
ECOG Performance Status	X								
Laboratory Procedures/Assessments: Analysis Performed by LOCAL Laboratory									
Pregnancy Test – Urine or Serum β-HCG	X ^d								
PT/INR and aPTT	X								
CBC with Differential	X	X ^f							
Comprehensive Serum Chemistry Panel (BMP)	X	X	X	X	X	X	X		
T3, FT4 and TSH ^b	X ^b		X ^b		X ^b		X ^b		
PFT's	X							X ^{c, f}	
Biopsy ^e		X ^g							

Treatment Cycle/Title:	Main Study Screening	1	2	3	4	5	6-16 (additional 16 cycles, for eligible patients)	Post MK-3475 Follow up	Survival Follow-Up (>2yrs) ^a
Scheduling Window (Days):	-28 to -1		± 3	± 3	± 3	± 3	± 3	Every 12 weeks post discon	Every 12 weeks
Blood Biomarker Testing ^e	X	X	X	X	X	X	X	X	
Efficacy Measurements									
Tumor Imaging (CT or PET scan) ^e	X				X		X ^f	X ^{e, f}	X ^{e, f}

- a. Can be done over the phone.
- b. Thyroid functions will be performed with every other MK-3475 cycle, if the first three test are WNL then it can be stopped.
- c. Optional biopsy after radiation treatment
- d. Within 2 weeks of study entry for women with child bearing potential.
- e. Imaging should be performed approximately every 12 weeks (± 4 weeks).
- f. standard of care
- g. Within 3 months of study entry

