Subjects should be assessed for possible ECIs prior to each dose. Lab results should be evaluated and subjects should be asked for signs and symptoms suggestive of an immune-related event. Subjects who develop an ECI thought to be immune-related should have additional testing to rule out other etiologic causes. If lab results or symptoms indicate a possible immune-related ECI, then additional testing should be performed to rule out other etiologic causes. If no other cause is found, then it is assumed to be immune-related.

ECIs that occur in any subject from the date of first dose through 90 days following cessation of treatment, or the initiation of a new anticancer therapy, whichever is earlier, whether or not related to the Merck’s product, must be reported within 24 hours to the Sponsor and to Merck Global Safety within 2 working days.

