7.2.4 Evaluating Adverse Events

An investigator who is a qualified physician will evaluate all adverse events according to the NCI Common Terminology for Adverse Events (CTCAE), version 4.0. Any adverse event which changes CTCAE grade over the course of a given episode will have each change of grade recorded on the adverse event case report forms/worksheets.

All adverse events regardless of CTCAE grade must also be evaluated for seriousness.

Table 10 Evaluating Adverse Events

An investigator who is a qualified physician, will evaluate all adverse events as to:

V4.0 CTCAE Grading	Grade 1	Mild; asymptomatic or mild symptoms; clinical or diagnostic observations only; intervention not indicated.
	Grade 2	Moderate; minimal, local or noninvasive intervention indicated; limiting age-appropriate instrumental ADL.
	Grade 3	Severe or medically significant but not immediately life-threatening; hospitalization or prolongation or hospitalization indicated; disabling; limiting self-care ADL.
	Grade 4	Life threatening consequences; urgent intervention indicated.
	Grade 5	Death related to AE
Seriousness	A serious adverse event is any adverse event occurring at any dose or during any use of Merck product that:	
	† Results in death ; or	
	† Is life threatening ; or places the subject, in the view of the investigator, at immediate risk of death from the event as it occurred (Note: This does not include an adverse event that, had it occurred in a more severe form, might have caused death.); or	
	† Results in a persistent or significant disability/incapacity (substantial disruption of one’s ability to conduct normal life functions); or	
	† Results in or prolongs an existing inpatient hospitalization (hospitalization is defined as an inpatient admission, regardless of length of stay, even if the hospitalization is a precautionary measure for continued observation. (Note: Hospitalization [including hospitalization for an elective procedure] for a preexisting condition which has not worsened does not constitute a serious adverse event.); or	
	† Is a congenital anomaly/birth defect (in offspring of subject taking the product regardless of time to diagnosis); or	
	Is a new cancer ; (that is not a condition of the study) or	

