All patients who receive any MK-3475 will be considered evaluable for response and will be included in the efficacy data set.

DLT is defined as any:

- DLTs are defined as any adverse event(s) considered related to the combination of MK-3475 plus radiation as described below:
 - Any \geq Grade 3 bronchospasm or other hypersensitivity reaction;
 - Any other \geq Grade 3 non-skin related adverse event with the exception of laboratory abnormalities;
 - Any Grade 4 laboratory abnormalities, except AST, ALT, or total bilirubin;
 - AST or ALT $> 8 \times$ ULN,
 - Total bilirubin $> 5 \times$ ULN;
 - Any other Grade 4 adverse event;
- 1. Any adverse event, laboratory abnormality or intercurrent illness which, in the judgment of the investigator, presents a substantial clinical risk to the subject with continued study drug dosing;
- 2. Subject experiences an allergic/infusion reaction while receiving study drug at a slower infusion rate due to a prior allergic/infusion reaction;
- 3. Any motor neurologic toxicity \geq Grade 3 regardless of causality;
- 4. Any \geq Grade 3 treatment-related sensory neurologic toxicity.
- 5. Drug related toxicity that prevents administration of MK-3475 for > 21 days from the scheduled dose
 - The time frame for DLT assessment will be within 22 days of therapy initiation.
 - Any grade 4 neutropenia (with or without fever and/or sepsis) or thrombocytopenia (with or without bleeding) lasting at least 1 week or longer (as defined by the NCI-CTC v4.0).
 - Any other grade 3 non-hematologic toxicity including symptoms/signs of vascular leak or cytokine release syndrome; or any severe or life-threatening complication or abnormality not defined in the NCI-CTCAE v4.0 that is attributable to the therapy.

9.2.1. *Statistical Analysis*

Descriptive statistics will be computed for all relevant outcomes, including toxicity, tumor response, PFS, OS, and biomarker response. Descriptive analysis will include a global assessment of patient outcomes for parts A and B separately. All patients receiving at least 1 treatment with MK-3475 will be included in the analysis.

9.2.2. *Demographics and Baseline Characteristics*

Frequency distributions of gender and race will be tabulated by dose/cohort. Summary statistics for age, body weight, height, and Body Mass Index (BMI) will be tabulated by dose/cohort.

9.2.3. *Safety Analyses*

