All recorded adverse events will be recorded per MDACC guidelines using CTCAE Version 4.0. Frequency of adverse events will be tabulated by grade, type, and dose/cohort. Relative frequencies and confidence intervals will also be constructed.

9.2.4. *Efficacy Analyses*

Efficacy data from part A and part B will be performed using the criteria below.

1. **Global irRC:** irRC that factors all lesions both index and non-index.
2. **In-Field irRC:** irRC in which only XRT-treated lesions will be considered and non-index lesions arising inside the XRT PTV
3. **Out-Field irRC:** irRC in which only non XRT-treated lesions will be considered and non-index lesions arising outside the XRT PTV

Time-to-event distributions for PFS and OS will be estimated via Kaplan-Meier analysis. Summary statistics will be computed along with confidence intervals. The limited sample size precludes formal statistical comparison with historical controls.

9.2.5. *Sample Size/Accrual Rate*

The maximum planned number of patients will be 80, with 40 patients being treated with LS-SCLC and 40 patients with ES-SCLC. It is estimated that approximately 1.5 patients per month (for both LS-SCLC and ES-SCLC) will be accrued over 26 months. With 40 patients, the probability of seeing at least one patient with toxicity if the true toxicity rate is 0.1 is 88%. The 95% binomial confidence interval for 6/20 (30%) extends from 15% to 52%.

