Thyroid disorders can occur at any time during treatment. Monitor patients for changes in thyroid function (at the start of treatment, periodically during treatment, and as indicated based on clinical evaluation) and for clinical signs and symptoms of thyroid disorders.

Grade 2 events (and Grade 3-4 hypothyroidism):

- Report as ECI if appropriate (see Table 1)
- Monitor thyroid function or other hormonal level tests and serum chemistries more frequently until returned to baseline values.
- Thyroid hormone and/or steroid replacement therapy to manage adrenal insufficiency.
- Therapy with pembrolizumab can be continued while treatment for the thyroid disorder is instituted.

- In hyperthyroidism, non-selective beta-blockers (e.g. propranolol) are suggested as initial therapy.
- In hypothyroidism, thyroid hormone replacement therapy, with levothyroxine or liothyronine, is indicated per standard of care.
- Consultation with an endocrinologist may be considered.

Grade 3 hyperthyroidism events:

- Report as ECI
- Hold pembrolizumab.
- Rule out infection and sepsis with appropriate cultures and imaging.
- Treat with an initial dose of methylprednisolone 1 to 2 mg/kg intravenously followed by oral prednisone 1 to 2 mg/kg per day. When symptoms improve to Grade 1 or less, steroid taper should be started and continued over no less than 4 weeks. Replacement of appropriate hormones may be required as the steroid dose is tapered.
- Permanently discontinue for inability to reduce corticosteroid dose to 10 mg or less of prednisone or equivalent per day within 12 weeks.

Grade 4 events:

- Report as ECI
- Discontinue pembrolizumab.
- Manage as per Grade 3

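### Flow chart footnote b lets scheduled thyroid testing end at cycle 4 or 6 of 16 to 32, although Appendix 13.4 asks for periodic thyroid monitoring on treatment

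*Combined protocol and SAP*

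**What the plan says.** In the section 6.1 flow chart, the T3/FT4/TSH row is marked at screening, cycle 2, cycle 4 and the column for cycles 6-16, which also covers the additional 16 cycles. Footnote b governs the row: "Thyroid functions will be performed with every other MK-3475 cycle, if the first three test are WNL then it can be stopped".

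Treatment is 16 three-weekly cycles (section 5.2, Table 2). Under section 2.2, Part A patients with disease control and no severe drug-related toxicity "will be eligible to get additional 16 cycles of MK-3475".

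Appendix 13.4, section 3.3 (hyperthyroidism and hypothyroidism), states that "Thyroid disorders can occur at any time during treatment" and asks that thyroid function be monitored "at the start of treatment, periodically during treatment, and as indicated based on clinical evaluation".

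For the analysis, section 9.2.3 says: "Frequency of adverse events will be tabulated by grade, type, and dose/cohort". Table 10 in section 7.2.4 describes Grade 1 as "Mild; asymptomatic or mild symptoms; clinical or diagnostic observations only; intervention not indicated".

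**The concern.** The flow chart and the appendix point in different directions. The appendix treats onset as possible throughout treatment and names three kinds of monitoring: baseline, periodic and clinically prompted. Once footnote b is used, only the clinically prompted kind is left for the rest of the course. Three early normal results do not rule out later onset.

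Safety is the primary objective. A Grade 1 thyroid abnormality may have no symptoms and can then be recognised only from a blood test. Without a scheduled test, such events may be found late or not at all, and the adverse event frequencies by grade, type and dose/cohort could be too low for later cycles. The rule also makes detection depend on early results: a patient with an early abnormal value stays on the testing schedule, while one with normal values may not.

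**Working it through.** The plan gives no figure to reproduce, so the check is a count from the flow chart.

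**Inputs**
- Thyroid panels at screening and at even-numbered cycles (section 6.1, row marks and footnote b).
- Three-week cycles, 16 planned (section 5.2, Table 2), and up to 32 for eligible Part A patients (section 2.2).
- Assumptions: no dose delays, all cycles completed, and testing stopped as soon as footnote b allows.

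**Timing.** Day 1 of cycle k falls on study day 21(k − 1) + 1.
- Cycle 2: 21 × 1 + 1 = day 22
- Cycle 4: 21 × 3 + 1 = day 64
- Cycle 6: 21 × 5 + 1 = day 106
- Cycle 16: 21 × 15 + 1 = day 316
- Cycle 32: 21 × 31 + 1 = day 652

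**Third test.** If screening counts, the three tests are screening, cycle 2 and cycle 4. If it does not, they are cycles 2, 4 and 6.

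**Panels scheduled.** Over 16 cycles: 1 + 8 = 9. Over 32 cycles: 1 + 16 = 17.

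| | Screening counts (last required panel: cycle 4) | Screening does not count (last required panel: cycle 6) |
|---|---|---|
| Panels droppable, 16 cycles | cycles 6, 8, …, 16: 6/9 = 67% | cycles 8, 10, …, 16: 5/9 = 56% |
| Cycles after last required panel, 16 cycles | 12/16 = 75% | 10/16 = 62.5% |
| Weeks from that panel to dose 16 | (316 − 64)/7 = 36 | (316 − 106)/7 = 30 |
| Panels droppable, 32 cycles | 14/17 = 82% | 13/17 = 76% |
| Cycles after last required panel, 32 cycles | 28/32 = 87.5% | 26/32 = 81% |
| Weeks from that panel to dose 32 | (652 − 64)/7 = 84 | (652 − 106)/7 = 78 |

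**Effect on dose finding.** Section 9.1 says: "The time frame for DLT assessment will be within 22 days of therapy initiation". The screening and cycle 2 (day 22) panels are required under either reading, so the DLT assessment and the MTD decision lose nothing.

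**Effect on adverse event counts.** The documents give no thyroid incidence or time-to-onset data, so the number of events missed cannot be estimated.

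**The case against.** The strongest reply is that there is no outright contradiction. The appendix sets no interval, number of tests or end point for periodic monitoring. A baseline test with two or three on-treatment panels could be said to satisfy it. Section 1 of the appendix calls its recommendations guidelines, subject to clinical judgment. Footnote b only permits stopping, and only after normal results, so an investigator who keeps testing complies with both texts.

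Other safeguards also remain. Section 7.2.3.2 says of events of clinical interest (ECIs): "Subjects should be assessed for possible ECIs prior to each dose". Adverse event review, examination, vital signs and chemistry are scheduled every treatment cycle, and section 7.1 allows unscheduled tests. Grade 3 or higher thyroid events would probably surface through these. For Grade 2 thyroid events, and for Grade 3-4 hypothyroidism, the appendix lets MK-3475 continue during treatment of the disorder, so late detection might change dosing little. Finally, the percentages are upper limits: they assume a full course and stopping at the first opportunity.

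Most of this stands and limits the weight of the point, but it does not remove it. The guideline caveat follows text on managing events judged drug-related, and the deference to protocol wording there concerns dose modification and treatment options rather than surveillance. Testing that ends at cycle 4 or 6 of 16 to 32 is hard to call periodic during treatment. None of the other safeguards requires a thyroid panel, and the chemistry row is separate from the thyroid row. A pre-dose review of laboratory results cannot detect an asymptomatic thyroid change if no thyroid test was done.

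**Conclusion.** The concern holds as a safety-monitoring weakness that should be corrected. Footnote b permits 56% to 67% of scheduled panels to be omitted over 16 cycles, and 76% to 82% over 32 cycles for eligible Part A patients. The range in each case reflects the unresolved status of the screening test. These figures describe how much of treatment can pass without a scheduled panel; they do not count events missed.

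The consequence is confined to mild or subclinical thyroid events, which could be detected late or under-recorded in the descriptive safety tables for later cycles. Dose escalation, the MTD and the sample size are unaffected. Confidence is medium, because the appendix leaves its monitoring interval undefined and the extent of under-recording is unknown.

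**What to change.** Delete the stopping clause from footnote b, so that T3, FT4 and TSH continue at every second cycle until the last dose of MK-3475. The existing row marks then apply to every patient on treatment and agree with Appendix 13.4, and whether screening counts no longer matters. A sparser continuing schedule could also be called periodic, but keeping the flow chart's own interval needs no new schedule. Testing after treatment ends is outside this change.

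The cost is a footnote edit and, per patient, up to 5 or 6 more panels over 16 cycles, or up to 13 or 14 over 32 cycles for eligible Part A patients. All fall at visits that already have a scheduled chemistry draw. No visits, endpoints or sample size need to change.
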